9.8.1 Day and Night Closed loop with Pump Suspend Feature

Those subjects randomised to closed loop intervention with pump suspend feature will receive training required for safe and effective use of the closed loop system and pump suspend feature. This will include training on connection and disconnection of the closed loop system, use of pump suspend feature and switching between closed loop and usual pump therapy. Written step by step guidance will also be provided. Competency on the use of closed loop system will be assessed by the study team. Only subjects who demonstrate competency on use of the system will be allowed to continue to the home study phase. Subject will use closed loop system under supervision from study staff. Subjects will be provided with a meal according to participant's choice and will be required to deliver meal bolus for the given meal. Subjects will be allowed to go home once competency assessment has been satisfactorily completed with the study staff. Participants are expected to use the closed loop and pump suspend feature at all times during the three months intervention period.

9.8.2 Sensor-Augmented Pump Therapy

Those subjects randomised to sensor augmented insulin pump therapy will receive training on the effective use of real-time CGM for optimisation of insulin therapy. Rest of the visit is identical to closed loop group as described in section 9.8.1.

9.9 Visit 6 – 24-48 hours after Starting Study Treatment

The subject will be contacted via telephone/e-mail or invited to attend the research centre approximately 24-48 hours after Visit 5 once study treatment has begun. US site must complete the contact by phone at minimum. The purpose of this visit will be to review the use of study devices and to provide any additional training required.

9.10 Visit 7 – 1 Week after Starting Study Treatment

The subject will be invited to attend the research centre approximately 1 week after Visit 5. The purpose of this visit will be to review the use of study devices and to provide any additional training required.

In the UK, the visit could be done via phone / e-mail. In the US in-person visit is mandatory.

9.11 Visit 8 – 2 Weeks after Starting Study Treatment

The subject will either be contacted via telephone/e-mail or seen in the clinic 1 week after Visit 7. The purpose of this visit would be to troubleshoot any problems. The subject is free to optimise further treatment but no active treatment optimisation will be undertaken by the study team.

9.12 Visit 9 – End of first month on Study Treatment

The subject will be contacted via telephone/e-mail or invited to attend the research centre approximately 1 month after start of study treatment to review the use of study devices. Any additional device training required will be provided. The subject is free to optimise further treatment but no active treatment optimisation will be undertaken by the study team.

9.13 Visit 10 – End of Second Month on Study Treatment

The subject will be contacted via telephone/e-mail or invited to attend the research centre approximately 1 month after Visit 9 to review the use of study devices. The subject is free to optimise further treatment but no active treatment optimisation will be undertaken by the study team.

9.14 Visit 11 – End of Study (3 months)

The subject will be invited to attend the research centre approximately 1 month after Visit 10. This would be the end of three months home study period and subjects will return to their normal diabetes care. Insulin pump and CGM device data will be downloaded. The subject will have a blood test for the HbA1c. Body weight measurement will be made. Subject will be asked to complete questionnaires as outlined in section 12.2. Subset of subjects/family members who completed CL intervention arm will be invited to perform a qualitative interview with the trained personnel. Subjects will be asked to return the study devices used, and will revert to their conventional insulin therapy by switching back to the insulin pump they were using before entering the study.

9.15 Participant Withdrawal Criteria

The following pre-randomisation withdrawal criteria will apply:

1. Subject is unable to demonstrate safe use of study insulin pump and / or CGM during run-in period as judged by the investigator
2. Subject fails to demonstrate compliance as mentioned in section 9.5.1 with study insulin pump and / or CGM during run-in period

The following pre- and post-randomisation withdrawal criteria will apply:

3. Subjects may terminate participation in the study at any time without necessarily giving a reason and without any personal disadvantage
4. Significant protocol violation or non-compliance
5. Any severe hypoglycaemia event related to use of the closed loop system
6. Two severe hypoglycaemia events unrelated to the use of the closed loop system
7. DKA unrelated to infusion site failure and related to the use of the closed loop system
8. Decision by the investigator or the sponsor that termination is in the subject's best medical interest
9. Subject becomes pregnant during the study period
10. Allergic reaction to insulin
11. Allergic reaction to adhesive surface of infusion set or glucose sensor
12. If patient continues to use pump suspend feature in the control group despite advice to the contrary

Subjects who are withdrawn for reasons stated in (4) to (12) will be invited to provide blood sample at the end of the planned study intervention for the assessment of HbA1c.

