Procedures for safety monitoring during trial	
Standard operating procedures for monitoring and reporting of all adverse events will be in place, including serious adverse events (SAE), serious adverse device effects (SADE) and specific adverse events (AE) such as severe hypoglycaemia.
 
Subjects will be asked to test and record blood or urine ketones if their finger prick glucose is above 14.0mmol/l (250mg/dl) in the morning on waking, as part of the safety assessment for hyperglycaemia.
 
A data safety and monitoring board (DSMB) will be informed of all serious adverse events and any unanticipated serious adverse device effects that occur during the study and will review compiled adverse event data at periodic intervals.

Criteria for withdrawal of patients on safety grounds

A subject, parent, or guardian may terminate participation in the study at any time without necessarily giving a reason and without any personal disadvantage. An investigator can stop the participation of a subject after consideration of the benefit/risk ratio. Possible reasons are:

1. Serious adverse events
2. Significant protocol violation or non-compliance
3. Failure to satisfy competency assessment
4. Decision by the investigator, or the sponsor, that termination is in the subject's best medical interest
5. Pregnancy, planned pregnancy, or breast feeding
6. Allergic reaction to insulin
7. Technical grounds (e.g. subject relocates)

3 Summary

The main study objective is to determine whether day and night automated closed loop glucose control combined with pump suspend feature will improve glucose control and reduce the burden of hypoglycaemia compared to sensor augmented insulin pump therapy alone.

This is an open-label, multi-centre, multi-national, single-period, randomised, parallel group design study, involving a three-month period of home study during which day and night glucose levels will be controlled either by a closed loop system combined with pump suspend feature (intervention group) or by sensor augmented insulin pump therapy (control group).

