11.2 Recording and Reporting of Adverse Events, Serious Adverse Events and Device Deficiencies

11.2.1 Monitoring Period of Adverse Events

The period during which adverse events will be reported is defined as the period from the beginning of the study (obtaining informed consent) until 3 weeks after the end of the study participation. Adverse events that continue after the subject's discontinuation or completion of the study will be followed until their medical outcome is determined or until no further change in the condition is expected. The follow up of AEs may therefore extend after the end of the clinical investigation; however no new AEs will be reported after the trial reporting period.

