14.3 Safety Analysis

Below safety outcomes will be tabulated by treatment group:

- Number of subjects with any diabetic ketoacidosis events
- Number of episodes of diabetic ketoacidosis events per subject and incidence rate per 100-person years
- Number of subjects with any severe hypoglycaemia events
- Number of episodes of severe hypoglycaemia events per subject and incidence rate per 100-person years
- Number of subjects with any severe hyperglycaemia events as defined by fingerprick glucose >16.7 mmol/l (>300 mg/dl) and plasma ketones >0.6 mmol/l
- Number of episodes of severe hyperglycaemia events per subject and incidence rate per 100-person years

Above safety data will be tabulated for all subjects in the two intervention periods, including drop-outs and withdrawals, irrespective of whether CGM data are available and irrespective of whether closed loop was operational. All adverse events will be listed for the entire study duration.

If there are enough observed events to allow formal statistical modelling for above safety outcomes, the following analyses will be conducted. The event rates will be compared using a Poisson regression model adjusting for random site effect. If outliers exist, a robust Poisson regression model will be used instead. Binary variables will be compared using a logistic regression model

adjusting for random site effect. Models involve severe hypoglycaemia events will also adjust for severe hypoglycaemia in the previous 6 months before enrolment.

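### The event-count withdrawal rules can end event collection sooner in the closed-loop arm, so severe hypoglycaemia episodes per subject lean slightly in its favour

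*Protocol*

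**What the plan says.** Section 9.15 of the protocol lists criteria that apply before and after randomisation. Three are triggered by events:

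- item 5: "Any severe hypoglycaemia event related to use of the closed loop system"
- item 6: "Two severe hypoglycaemia events unrelated to the use of the closed loop system"
- item 7: "DKA unrelated to infusion site failure and related to the use of the closed loop system"

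Item 8 is discretionary and names no arm: "Decision by the investigator or the sponsor that termination is in the subject's best medical interest". The synopsis adds: "An investigator can stop the participation of a subject after consideration of the benefit/risk ratio", and lists serious adverse events among the possible reasons.

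Participants withdrawn under items 4 to 12 "will be invited to provide blood sample at the end of the planned study intervention for the assessment of HbA1c". Section 9.15 specifies no other follow-up for them. Section 11.2.1 has new adverse events reported "until 3 weeks after the end of the study participation".

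Section 14.3 tabulates by arm, for all subjects including withdrawals, the number with any event and the "Number of episodes of severe hypoglycaemia events per subject and incidence rate per 100-person years", with matching entries for DKA. If there are enough events, rates are compared by Poisson regression and binary outcomes by logistic regression, both with a random site effect.

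**The concern.** The rules carry no arm label, but an event related to the closed loop can occur only where the closed loop is used. Items 5 and 7 can therefore end participation at a first event in one arm only. Three weeks later the collection of new events for that person stops. Any further episode before the planned week 12 is lost, and this can happen one event earlier on closed loop than on control.

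Relatedness is judged by the site investigator (11.2.2, 11.2.5) in an open-label trial, so an unblinded judgement helps to decide how long events are collected. Severe hypoglycaemia is named in the safety objective (5.2), and the lean favours the system under test. An analysis plan cannot recover events that were never collected, so the collection window is a matter for the protocol.

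**Working it through.** The protocol gives no figure for these safety outcomes, so there is none to reproduce.

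**1. The rules by arm**

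| Trigger | Closed loop | Control |
|---|---|---|
| Related severe hypoglycaemia (item 5) | at 1 event | cannot occur |
| Unrelated severe hypoglycaemia (item 6) | at 2 events | at 2 events |
| Related DKA, not infusion site failure (item 7) | at 1 event | cannot occur |
| Discretion (item 8, synopsis) | any time | any time |

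**2. Inputs.** The treatment period is 84 days (14.6), so T = 84/365.25 = 0.230 years. Section 4 gives one severe episode per year for the average patient. That is a high value here, because section 7.3 excludes anyone with an episode in the previous 6 months. Assumptions: 42 per arm (no allocation ratio is stated), a lower rate of 0.3 per year, between-person (gamma) variance of 2 to 5, and half or all closed-loop events judged related. True risk is the same in both arms, and discretionary withdrawal is left out.

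**3. Closed form: one common constant rate r, all closed-loop events related, no tail.** With λ = rT:

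- Expected episodes if observation stops at the first event: 42(1 − e^−λ).
- If it stops at the second event: 42[(1 − e^−λ) + 1 − e^−λ(1 + λ)].
- At r = 1, λ = 0.230: 8.63 against 9.58 episodes, ratio 0.90. Full follow-up would give 42 × 0.230 = 9.66.
- At r = 0.25: 2.35 against 2.41, ratio 0.97.
- Expected person-years are the episodes divided by r: at r = 1, 8.63 and 9.58. The rate is 1.00 in both arms and the rate ratio is 1.00.

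Under a common constant rate the cut-off lowers episodes per subject but not the person-year rate, because time is lost along with events.

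**4. Simulation with participants who differ in risk** (2 million per cell). The range in each cell runs from variance 2 to variance 5. The tail adds events and time for up to 21 days after withdrawal, no later than day 84, in both arms.

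| Rate per year | Share judged related | Rate ratio, no tail | Rate ratio, 3-week tail |
|---|---|---|---|
| 0.3 | all | 0.94 to 0.89 | 0.97 to 0.93 |
| 0.3 | half | 0.97 to 0.94 | 0.98 to 0.97 |
| 1.0 | all | 0.87 to 0.79 | 0.92 to 0.87 |
| 1.0 | half | 0.94 to 0.89 | 0.96 to 0.94 |

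Figures are good to about 0.01. With the tail and all events related, the episodes-per-subject ratio is about 0.95 to 0.91 at 0.3 per year and 0.88 to 0.83 at 1 per year. Per 42 participants the closed-loop shortfall is:

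- at 0.3 per year: 2.88 − 2.75 = 0.13 to 2.85 − 2.61 = 0.24 episodes
- at 1 per year: 9.33 − 8.20 = 1.13 to 8.80 − 7.35 = 1.45 episodes

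The proportion with any event is equal in the two arms in every cell, apart from simulation error, because no rule acts before the first event.

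**5. Against the noise.** At 0.3 per year one arm expects 0.3 × 9.66 = 2.9 episodes. With about 2.6 in the other, the standard error of the log rate ratio is √(1/2.9 + 1/2.6) = 0.85. The largest bias in the tail column at that rate is ln 0.93 = −0.07.

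**The case against.** The case against giving this much weight is strong, and most of it stands.

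- Section 14.3 makes its modelling conditional on enough events. At about 3 episodes per arm the Poisson comparison would probably not be run. Section 14.9 does name a repeated-measures logistic comparison without that condition. In any case, episodes and rates are tabulated by arm and will be read as safety evidence.
- The unaffected comparison, participants with any event, is already in the plan. Withdrawals are included, so the triggering event is counted.
- The 3-week tail recovers roughly 35% to 50% of the lean, although those events occur off the assigned treatment.
- The variance is an assumption with no support in the documents. Without it the rate ratio is 1.00.
- Definitions of person-time may properly sit in the separate analysis plan. The reporting window does not.

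A reader might infer that controls leave only after two severe hypoglycaemias. The documents do not support that. Item 8 sets no event count, the synopsis lists serious adverse events as a reason to stop participation, and 11.2.3 treats every severe hypoglycaemia as serious, so a control can be withdrawn after one. Item 6 also covers unrelated events on closed loop. Nor does every DKA on closed loop trigger withdrawal: item 7 requires relatedness and excludes infusion site failure.

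**Conclusion.** The point holds in a limited form and is minor. The event-count rules differ in practice by arm, and no collection of severe hypoglycaemia or DKA is specified after the 3-week tail. Episodes per subject therefore lean towards closed loop under equal true risk.

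A reader might go further and call the incidence rates biased as such. That needs differences in underlying risk between participants, since person-time is cut along with events. At 0.3 episodes per year the lean is about 0.1 to 0.25 episodes per 42 participants even if every closed-loop event is judged related. At 1 per year it is just over one episode.

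These sizes rest on the assumed rates, variance, share judged related and 42 per arm. Discretionary withdrawal of controls after one event would narrow the gap. No size was worked out for DKA; only the direction follows from item 7. The any-event comparison is not affected.

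**What to change.** Leave the clinical withdrawal rules as they are.

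**Main change (11.2.1 and 9.15).** State that severe hypoglycaemia and DKA are collected for every randomised participant up to the planned week-12 date, whether or not they have been withdrawn, and flagged as on or off study treatment. The contact already used for the week-12 HbA1c invitation can serve.

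**Supporting change (14.3).** Name the already planned comparison of participants with any event as the lead between-arm safety comparison for severe hypoglycaemia and DKA. Show episodes and rates beside it with the person-time in each arm.

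The cost is some wording and one question at an existing contact. Off-treatment events must be reported separately, and participants who decline further contact will still be missing.

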9.16 Study Stopping Criteria

The study may be stopped if three consecutive participants withdraw on safety grounds or on the advice of an independent Data Safety and Monitoring Board (DSMB).

9.17 Support telephone line

There will be a 24-hour telephone helpline to the local research teams for subjects in case of any technical device or problems related to diabetes management such as hypo- or hyperglycaemia.

9.18 Subject reimbursement

The study will provide the CGM device, insulin pump, closed loop components, related consumables, and glucose test strips. A study fee will be paid to reflect local practice. The amount

paid will be specified in the participant information sheet and REC/IRB application form. Reasonable travel expenses will also be reimbursed. After completing the study, subjects will not keep the study devices. They will revert to their conventional insulin pump therapy.

10 Endpoints

10.1 Primary Endpoint

The primary outcome is the time spent in the target glucose range from 3.9 to 10.0 mmol/l (70 to 180mg/dl) based on CGM glucose levels during the 12 week free living phase.

10.2 Secondary Endpoints

Secondary endpoints include:

- HbA1c at 12 weeks
- Time spent below target glucose (3.9mmol/l) (70mg/dl)
- Time spent above target glucose (10.0 mmol/l) (180 mg/dl)
- Average, standard deviation, and coefficient of variation of glucose levels
- The time with glucose levels < 3.5 mmol/l (63mg/dl) and <2.8 mmol/l (50mg/dl)
- The time with glucose levels in the significant hyperglycaemia (glucose levels > 16.7 mmol/l) (300mg/dl)
- Total, basal and bolus insulin dose
- AUC of glucose below 3.5mmol/l (63mg/dl)
- Number of pump suspend events (applicable to intervention arm)
- Change in body weight from screening to end of study

Glucose endpoints will be based on sensor glucose.

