9.6 Randomisation

Eligible subjects who have gained confidence in the use of the study insulin pump and the study CGM system, as assessed by the research team, will be randomised centrally using a randomisation based on a computer-generated random code. Randomisation will take place centrally, with an independent person being responsible for the randomisation sequence. Subjects will be allocated to one of the two intervention arms: three months use of day and night closed loop combined with pump suspend feature or three months use of sensor augmented insulin pump therapy without pump suspend feature.

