9.7 Baseline Qualitative Interview

A subset of subjects/guardians randomised to the use of day and night closed loop with pump suspend feature will be invited for a qualitative interview (face to face or telephone interview) at a mutually convenient time, see section 12.2.2. Whenever possible, the interview will occur before Visit 8.

9.8 Visit 5 (Initiation of Study Treatment; within 1 Week of Visit 4 and at least 4 Weeks after Visit 3)

Subject will arrive at the clinical facility at the agreed time. Urine pregnancy test will be performed on arrival for all females of child bearing age and all subjects will have a blood test for HbA1c. Body weight measurement will be made. Subjects will be provided with necessary training on use of study devices according to randomisation. Competency assessment will be made. During the three months home treatment period, the subject will be asked to upload the study insulin pump and CGM at weekly intervals.

During the three months home closed loop treatment, the subject is allowed to drive while adhering to usual precautions and country specific rules and regulations.

During the first 2 weeks of each study period subject will be advised against international travel. During the rest of the study period, participants are allowed to travel internationally according to guidelines provided in the participant information sheet.

Subjects will be provided with 24 hour telephone helpline and will also be given written instructions about dealing with low and high glucose at home and when to contact study team. It is also possible to conduct Visit 8 in subject's home.

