12.1.3 Insulin Pump Data

Data from the study insulin pump will be downloaded periodically during each intervention by the participant.

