13.3 Insulin Pump used during Run-in and Control Intervention

During sensor augmented insulin pump therapy, similar insulin pump device will be used (Medtronic 640G) but pump suspend feature will be turned off.

During run-in and to download insulin and sensor data during the interventional and control periods, Medtronic CareLink® Therapy Management Software or similar will be used.

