14.6 Per-protocol Analysis

Per-protocol analysis will be performed to replicate the primary analysis limited to subjects who meet the following criteria:

- CL + LGS arm
 - Closed loop active for at least 80% of the time when CGM data were available
 - CGM data available for at least 50% of the 84 day study period
- SAP arm
 - CGM data available for at least 50% of the 84 day study period.

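### The per-protocol rule checks receipt of assigned treatment in the closed-loop arm but not in the control arm, so a control who used pump suspend can count as treated per protocol

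*Protocol*

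**What the plan says.** Protocol Section 9.6 defines the control arm as "three months use of sensor augmented insulin pump therapy without pump suspend feature"; the synopsis describes it the same way. Section 13.3 says that for controls a "similar insulin pump device will be used (Medtronic 640G) but pump suspend feature will be turned off". Section 9.15 lists as withdrawal criterion 12: "If patient continues to use pump suspend feature in the control group despite advice to the contrary".

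Suspend use is followed in one arm only. Section 10.2 lists "Number of pump suspend events (applicable to intervention arm" among the secondary endpoints. Section 10.4 covers closed loop with suspend in the closed-loop arm, and CGM use in both arms. Section 14.4 analyses CGM use in both arms and closed-loop use in the closed-loop arm.

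Section 14.6 sets two conditions for the closed-loop arm: closed loop active for at least 80% of the time with CGM data, and "CGM data available for at least 50% of the 84 day study period". For the control arm it sets only the second.

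Pump data are collected in both arms. In Section 9.8, "the subject will be asked to upload the study insulin pump and CGM at weekly intervals", and Section 12.1.3 says "Data from the study insulin pump will be downloaded periodically during each intervention by the participant".

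**The concern.** A per-protocol set is meant to hold subjects who received what they were assigned. What separates the control treatment from ordinary use of this pump with CGM is that suspend is off. The protocol treats persistent departure from that as grounds for withdrawal, yet Section 14.6 does not ask whether suspend was off. The two sections do not fit together.

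At stake is whether the per-protocol analysis can be read as a comparison with the comparator the protocol defines. There is also a matter of interpretation. Reducing the burden of hypoglycaemia is a stated purpose of the trial, and suspend acts directly on hypoglycaemia. Without a planned summary of control suspend use, a reader of the hypoglycaemia results has no prespecified table showing how far the comparator was delivered.

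**Working it through.** **1. What each arm must show under Section 14.6.**
- CGM minimum, both arms: 0.50 × 84 = 42 days.
- Closed-loop arm at that minimum: 0.80 × 42 = 33.6 days with closed loop active.
- Control arm at that minimum: 0 days with suspend shown to be off.

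**2. Which controls with suspend use can remain in the set.**
- Use that stops after advice does not meet criterion 12, which concerns those who continue. Such a control stays in the trial and in the per-protocol set.
- Undetected use also leaves the control in the set.
- A control withdrawn under criterion 12 after supplying 42 days of CGM data still meets the Section 14.6 condition. Section 9.15 says only that "Subjects who are withdrawn for reasons stated in (4) to (12) will be invited to provide blood sample" for HbA1c; it does not remove CGM data already collected. Section 14.1 does not truncate data for deviations, and the per-protocol analysis replicates that analysis in a restricted set.

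**3. The plan's own sample size, as a base for scale.** Section 14.10 gives a difference of 10 and an SD of 14.5 percentage points, 85% power and two-sided 5%. With 1:1 allocation (assumed, since no ratio is stated):

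n per arm = 2 × (1.960 + 1.036)² × 14.5² / 10² = 37.8, rounded up to 38, so 76 in total. The stated figure is reproduced. Power is 85.2% at 38 per arm and 88.5% at 42 per arm.

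**4. Effect on the primary outcome under assumed contamination.** Let c be the share of controls using suspend and f the share of the 10-point effect they would gain from it. Neither is in the protocol. The diluted difference is 10 × (1 − c × f).

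| c | f | Difference | Power, n = 76 | Power, n = 84 |
|---|---|---|---|---|
| 5% | 0.25 | 9.9 | 84.3% | 87.7% |
| 10% | 0.5 | 9.5 | 81.5% | 85.1% |
| 20% | 0.5 | 9.0 | 77.2% | 81.2% |
| 20% | 1 (extreme) | 8.0 | 67.2% | 71.5% |

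**5. Effect on hypoglycaemia under assumed contamination.** Section 4.3 cites a large trial of threshold suspend with nocturnal hypoglycaemia AUC of 54.4 (SD 66.6) against 87.0 (SD 110.7).
- Relative reduction: (87.0 − 54.4) / 87.0 = 37.5%.
- With suspend on for 5%, 10% or 20% of control time (assumed), control AUC falls by 1.9%, 3.7% or 7.5%.
- Treating the cited SDs as per-subject SDs (also assumed), the pooled SD is √((66.6² + 110.7²) / 2) ≈ 91. With 42 per arm, the standard error of the difference is 91 × √(2/42) ≈ 20.
- At 20%, the control mean moves by 0.20 × 32.6 ≈ 6.5 units, about one third of a standard error.

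**The case against.** The strongest reply is that limiting the suspend-event endpoint to the intervention arm is correct: suspend is part of that treatment and is off for controls. This stands. Section 14.2 plans a between-arm comparison of the outcomes in Section 10.2, so the restriction also prevents a meaningless test against an arm where the count should be zero by design.

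Three stronger readings are tempting, and the protocol does not support them.
- A reader might infer that the sponsor expects controls to use suspend. Criterion 12 is a contingency, listed with pregnancy and allergic reactions; it does not predict use.
- A reader might infer that control suspend use would never come to light. Pump data are uploaded in both arms and reviewed at control visits, and Section 21 requires deviations to be logged and signed off. What is absent is a planned summary.
- A reader might infer that a null hypoglycaemia result could not be told apart from contamination. The data to examine it would exist, and step 5 suggests that even 20% use would shift the control mean by only a fraction of a standard error.

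It can also be said that the per-protocol analysis repeats only the time-in-range comparison, so changing its set does not alter the hypoglycaemia analyses. That stands, and it is why the descriptive table is needed as well. A suspend-off rule with no threshold would exclude a control for a single activation, possibly one prompted by hypoglycaemia, and so add post-randomisation selection. That argues for a tolerance.

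Finally, Section 14.1 announces a separate analysis plan, which could hold an adherence table. But the protocol itself writes out the per-protocol criteria, and they are unequal as written.

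**Conclusion.** The point holds as a badly fixed definition. Section 14.6 verifies receipt of closed loop in one arm and only data availability in the other, which does not fit the control definition in Section 9.6 or criterion 12 in Section 9.15. No planned endpoint or utility measure summarises suspend use in controls.

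Its size is modest. Low contamination costs the primary comparison little power, and if suspend helps controls, any bias runs toward no difference. The dilution figures of about 2% to 7% of control hypoglycaemia AUC are illustrative: the shares of control time are assumed, and a nocturnal effect from another trial is carried over to whole-day AUC. The actual share is not known from the protocol. The sample size is not in question.

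**What to change.** 1. In Section 14.6, add a treatment-receipt criterion for the control arm: suspend feature off for at least a prespecified share of the time with CGM data. A value of 80% would mirror the closed-loop criterion and avoids excluding a control for brief use.
2. In Section 14.4, add a descriptive table of control-arm suspend use: subjects with any use, number of events and duration, taken from the pump uploads.
3. Keep the intervention-arm restriction in Section 10.2, so that suspend events stay out of the between-arm comparison in Section 14.2.
4. Leave the intention-to-treat analysis unchanged.

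The cost is one sentence, one table and possibly a slightly smaller control per-protocol set. The time-based criterion assumes that the uploads show when the feature was on as well as when it triggered; this should be confirmed before the wording is settled.
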